13.4 Local Tolerability Assessments

The investigator's assessment of the application site reaction will be summarized by visit using both categorical methods (number and percentage of subject with each score) as well as continuous methods (e.g., mean, standard deviation, etc.)

Local tolerability (burning/stinging sensation) assessed by the subject will be summarized using number and percentage similarly.

	STATISTICAL ANALYSIS PLAN, Version 1.0
Protocol Number: ARQ-151-312	Sponsor: Arcutis Biotherapeutics, Inc.

13.5 Patient Health Questionnaire Depression Scale (PHQ-8) and Patient Health Questionnaire Depression Scale (Modified PHQ-A)

The Modified PHQ-A Assessment will be performed in adolescent subjects (12-17 years old, inclusive; question 9 has been removed since that is better evaluated by use of the C-SSRS tool).

The PHQ-8/Modified PHQ-A score is the sum of the responses for the questions, each question ranging from 0 (Not at all) to 3 – (Nearly every day). Five severity categories of depression are defined as follows:

- None Minimal depression (0 to 4)
- Mild depression (5 to 9)
- Moderate depression (10 to 14)
- Moderately severe depression (15 to 19)
- Severe depression (20 to 24)

The score will be set to missing in case of at least one missing value. The number and percentage of subjects in each category will be summarized by treatment and visit. A summary of the shifts in depression category from baseline to each study visit will also be provided.

13.6 Children's Depression Inventory 2 (CDI-2)

The CDI-2 Assessment will be performed in children subjects (6-11 years old, inclusive).

The observed values and changes from baseline will be calculated for CDI-2 total score and the 2 scales, i.e., emotional problems and functional problems, and will be summarized descriptively by treatment group and visit.

The CDI-2 total score will be categorized as follows:

- 1. Normal: Male Score < 22, Female Score < 21
- 2. Elevated: $22 \le Male Score < 32$, $21 \le Female Score < 32$
- 3. Very Elevated: Male or Female Score \geq 32.

The proportion of subjects that meeting the criteria will be summarized by treatment group and visit.

A summary of the shifts in CDI-2 category from baseline to each study visit will also be provided.

	STATISTICAL ANALYSIS PLAN, Version 1.0
Protocol Number: ARQ-151-312	Sponsor: Arcutis Biotherapeutics, Inc.

13.7 Columbia-Suicide Severity Rating Scale (C-SSRS)

The Columbia-Suicide Severity Rating Scale (C-SSRS) is a questionnaire used (for adolescents and adults 12 years old and older) for suicide assessment developed by multiple institutions, including Columbia University. The C-SSRS prospectively assesses Suicidal Ideation and Suicidal Behavior. At the Screening study visit, "Baseline/Screening" version of the C-SSRS will be used. This version assesses Suicidal Ideation and Suicidal Behavior during the subject's lifetime and during the past 6 months. For the Screening visit, "lifetime" experience of the subject with Suicidal Ideation and Suicidal Behavior will be summarized. On all subsequent visits, the "Since Last Visit" version will be used (Baseline/Day 1, Week 1/Day 8, Week 2/Day 15 or Week 4/Day 29).

Tables will include results from the Suicidal Ideation and Suicidal Behavior sections of the C-SSRS. Frequencies and percentages of subjects with a response of "Yes" at any point on the Suicidal Ideation and Suicidal Behavior items will be summarized by study visit and treatment group.

13.8 Physical Examination

The number and percentage of subjects with normal and abnormal findings in the physical examination will be presented by body system and treatment group at each study visit.

14 PHARMACOKINETICS ANALYSIS

Concentration data will be summarized by visit by age group (<18 vs. >=18) and overall, for active treatment group using descriptive statistics, reporting n, mean, standard deviation, median, Q1, Q3, minimum, and maximum, and geometric statistics including geometric mean and coefficient of variation. For computation of mean plasma concentrations, data that are below the limit of quantification (BLQ) will be set to 0.0001. The PK population will be used for these analyses.

PK data will be presented in the listing.

	STATISTICAL ANALYSIS PLAN, Version 1.0
Protocol Number: ARQ-151-312	Sponsor: Arcutis Biotherapeutics, Inc.

16 APPENDICES

Appendix 1

Output Conventions

TLF will be generated using SAS® and will be displayed on letter size paper with landscape orientation, 1-inch margins and 9 pt. Courier New font.

The header section will comprise the sponsor's name, the protocol number, the delivery description, the data cut-off date (if applicable), the TLF number, the TLF title, the analysis set, and the page number (Page X of Y). The footer section will include the TLF footnotes, the CRO's name, the date and time of the execution of the program, and the name of the program.

P-values equal to or above 0.0001 will be reported to 4 decimal places; p-values less than 0.0001 will be reported as "<0.0001"; p-values greater than 0.9999 will be reported as ">0.9999".

The mean, median, geometric mean will be displayed to one more decimal place than the original value; Q1, Q3, minimum and maximum will keep the same number of decimal places as the original value; standard deviation, standard error, CV and CI will be displayed to two more decimal places than the original value. If derived parameters are to be summarized, the number of decimals of the derived values is to be chosen on a case-by-case basis, but the rule above applies.

For categorical summary tables, percentages will be reported to one decimal place. Percentages between 0 and 0.1 (both exclusive) will be displayed as "<0.1". The denominator for each percentage will be the number of subjects within the population per treatment group unless otherwise specified.

Listings will be ordered by treatment group, subject number, date and visit (where applicable). Imputed dates will not be presented in the listings.

Dates & Times Format

Date and time (if available) will be presented in the format yyyy-mm-dd/hh:mm.

Presentation of Treatment Groups

When applicable, study treatments will be represented as follows in the different outputs:

Study Treatment Full Name	Study Treatment Output Name
Roflumilast cream 0.15%	Roflumilast Cream 0.15%
Vehicle cream	Vehicle

	STATISTICAL ANALYSIS PLAN, Version 1.0
Protocol Number: ARQ-151-312	Sponsor: Arcutis Biotherapeutics, Inc.

Appendix 2

Algorithm for Imputation of Start/End Date and Time of Adverse Events and Prior/Concomitant Medications

Event Start Date Imputation

- Imputation of event end date should be done before imputation of event start date.
- Completely missing: Impute to the first study treatment date.
- Missing day and month: Impute to January 1st, unless year is the same as year of first study treatment dose date then impute to the first study treatment date.
- Missing day: Impute to the 1st day of the month, unless month and year are the same as month and year of first study treatment dose date then impute to the first study treatment date.
- If imputed event start date is after event end date (imputed or not), set the event start date to the imputed event end date.

Event Start Time Imputation (for Adverse Events only)

Imputation of event end time should be done before imputation of event start date.

[figure not shown]
- If the event date is not the same as the first dose date or time part of the first dose date is missing, impute to 00:00.
- If the event date is the same as the first dose date and event occurred prior to study drug application (as flagged in CRF), impute to 00:00.
- If the event date is the same as the first dose date and event did not occur prior to study drug application (as flagged in CRF), impute to time part of first dose date.
- If the event start date is equal to event end date and imputed event start time is after event end time (imputed or not), set the event start time to the imputed event end time.

Event End Date Imputation

- Completely missing (and not flagged as "ongoing"): Impute to the last contact date.
- Missing day and month: Impute to December 31st, unless year is the same as last contact date then impute to the last contact date.
- Missing day: Impute to the last day of the month, unless year and month are the same as year and month of last contact date then impute to the last contact date.

Event End Time Imputation (for Adverse Events only)

Impute to 23:59.

Electronic Record and Signature Disclosure: Accepted: 08-Jun-2022 | 12:08 ID: 3f347f78-8c69-41a3-ab01-f48a0581f66e

In Person Signer Events	Signature	Timestamp
Editor Delivery Events	Status	Timestamp
Agent Delivery Events	Status	Timestamp
Intermediary Delivery Events	Status	Timestamp
Certified Delivery Events	Status	Timestamp
Carbon Copy Events	Status	Timestamp
Witness Events	Signature	Timestamp
Notary Events	Signature	Timestamp
Envelope Summary Events	Status	Timestamps
Envelope Sent Certified Delivered Signing Complete Completed	Hashed/Encrypted Security Checked Security Checked Security Checked	07-Jul-2022 07:05 07-Jul-2022 21:49 07-Jul-2022 21:50 07-Jul-2022 21:50
Daymant Frants		
Payment Events	Status	Timestamps

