3 STUDY DESIGN

3.1 Overall Design

[figure not shown]
This is a Phase 3, parallel group, double blind, vehicle-controlled study in which Roflumilast cream 0.15% or vehicle is applied QD x 4 weeks to subjects with mild to moderate atopic dermatitis.

- Upon determination of eligibility, subjects will be randomized 2:1 to either Roflumilast cream 0.15% or matching vehicle cream. The randomization will be stratified by vIGA-AD score at baseline ('Mild' vs. 'Moderate') and by study site.
- At the Week 4 visit, subjects may be eligible to enroll in an open label extension study (ARQ-151-313) in which they will receive Roflumilast cream 0.15% QD.

The trial design is represented schematically in Figure 1.

	STATISTICAL ANALYSIS PLAN, Version 1.0
Protocol Number: ARQ-151-312	Sponsor: Arcutis Biotherapeutics, Inc.

Figure 1 Study Schema

A Phase 3, 4-Week, Parallel Group, Double Blind, Vehicle-Controlled Study of the Safety and Efficacy of ARQ-151 Cream 0.15% Administered QD in Subjects with Atopic Dermatitis

Approximately 650 subjects with atopic dermatitis will be randomized 2:1 to receive either:

• Roflumilast cream 0.15% or Vehicle cream

Subjects will have ≥3% BSA involvement (excluding the scalp, palms, soles) with a vIGA-AD score of '2' (mild) or '3' (moderate) for study entry

Up to 50% of the subjects will be \geq 18 years old

	STATISTICAL ANALYSIS PLAN, Version 1.0
Protocol Number: ARQ-151-312	Sponsor: Arcutis Biotherapeutics, Inc.

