3.2 Schedule of Events

Table 1 Schedule of Visits and Assessments

Study Procedure	Screen	Baseline Day 1	Wk 1 Day 8	Wk 2 Day 15	Wk 4 Day 29 / ET
Visit	1	2	3	4	5
Visit Window	-30 days	N/A	+/- 3 days	+/- 3 days	+/- 3 days
Informed consent/assent	X				
Demographics	X				
Medical and surgical history	X				
Physical examination ^a	X	X			X
I/E criteria	X	X			
Hematology, Serum Chemistries, and Urine Analysis ^b	X^b	X^{b}			X^{b}
Vital signs, height, weight ^c	X	X	X	X	X
vIGA-AD, EASI, BSA, SCORAD ^d	X	X	X	X	X
WI-NRS pruritus ^e	X	X	X	X	X
POEMf	X	X	X	X	X
Local Tolerability Assessment ^g		X	X	X	X
CDI-2, PHQ-8, PHQ-A, C-SSRS ^h	X	X	X	X	X
DLQI, CDLQI, DFI ⁱ	X	X	X	X	X
Medical Photography ^j		X	X		X
Serum pregnancy test (FOCBP only)	X				
Urine pregnancy test ^k		X	X	X	X
PK draws ¹					X
Drug/vehicle application in clinic ^m		X	X	X	
Dispense/Re-dispense study medication kit ⁿ		X	Xº	Xº	X°
Dispense/review diary	X	X	X	X	X
Weigh study medication kit ^p		X	X	X	X
Compliance determination ^q			X	X	X

	STATISTICAL ANALYSIS PLAN, Version 1.0
Protocol Number: ARQ-151-312	Sponsor: Arcutis Biotherapeutics, Inc.

Study Procedure	Screen	Baseline Day 1	Wk 1 Day 8	Wk 2 Day 15	Wk 4 Day 29 / ET
Adverse event assessment ^r	X	X	X	X	X
Concomitant medications	X	X	X	X	X
Study Exit ^s					X

- a Limited physical examination: skin (including assessment of Fitzpatrick skin type at Screening only), lungs, and heart only
- b For all subjects entering this study under Amendment 2, to be collected at Screening, but subsequent samples will be collected only for subjects ≥12 years old (Baseline/Day 1 and Week 4/Day 29/ET). For subjects 12 to 18 years of age, if Baseline/Day 1 is within 3 weeks of Screening, the Screening results may be used.
- ^c Height will be collected at Screening only. Weight should be obtained using a calibrated weight scale and the same scale should be used for a subject throughout the duration of the study. The subject should remove shoes and heavy clothing (sweaters or jackets), and empty pockets. The subject should stand with both feet in the center of the scale with their arms at their side and hold still. Record the weight to the nearest decimal fraction (for example, 25.1 kilograms). For subjects <18 years of age, measure the weight in triplicate and report the average weight in EDC. A 5% or greater weight loss (whether or not intentional or other explained) should be reported to the medical monitor.

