13 SAFETY ANALYSIS

Safety analyses will be conducted using the safety population. Subjects will be analyzed based on the treatment received and the stratum they belong to.

No formal inferential statistics will be performed on safety assessments.

Also, treatment-emergent adverse events by SOC and PT table and summary of weight change will be presented by treatment groups for age 6 to 17 years and \geq 18 years separately.

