13.2 Clinical Laboratory

Descriptive statistics for the observed values in chemistry, hematology, and quantitative urinalysis, change from baseline and percent change from baseline values will be presented by treatment group at each scheduled visit. For qualitative urinalysis data, the number and percentage of the subjects for each level of result by treatment at each scheduled visit will be provided.

Shift tables from baseline to each postbaseline assessments describing shifts to out-of-normal range will be provided for chemistry, hematology, and qualitative urinalysis. Only subjects with a baseline result and a result at the specified visit for the parameter will be considered.

Listings of abnormal laboratory will be provided for each parameter where a subject had at least one abnormal result.

Laboratory data will be presented in SI units.

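### SAP Appendix 1 makes the whole arm the default denominator, and the age-restricted safety measures (above all C-SSRS) do not override it, so their percentages would be diluted by subjects who were never assessed

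*SAP*

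**What the plan says.** **The default.** SAP Appendix 1 (Output Conventions) states: "The denominator for each percentage will be the number of subjects within the population per treatment group unless otherwise specified".

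**The population.** SAP Section 13 states: "Safety analyses will be conducted using the safety population". Section 4.7 defines that population as enrolled and dosed subjects, with no age limit and no requirement to have completed any instrument. Section 4 defines no age-specific safety set.

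**Who is assessed.** Footnote h of the SAP schedule (Section 3.2) gives C-SSRS to subjects aged 12 and over, PHQ-8 to adults, PHQ-A to ages 12-17 and the CDI-2 parent report to ages 6-11. Footnote b says that, for subjects entering under Amendment 2, laboratory samples are taken at Screening but "subsequent samples will be collected only for subjects ≥12 years old".

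**What is tabulated.**
- PHQ-8 and PHQ-A (13.5): "The number and percentage of subjects in each category will be summarized by treatment and visit".
- CDI-2 (13.6): "The proportion of subjects that meeting the criteria will be summarized by treatment group and visit".
- C-SSRS (13.7): subjects answering Yes "at any point on the Suicidal Ideation and Suicidal Behavior items will be summarized by study visit and treatment group".
- Urinalysis (13.2): "For qualitative urinalysis data, the number and percentage of the subjects for each level of result by treatment at each scheduled visit".

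None of these sentences names a denominator. Elsewhere the SAP does name one where it wants a departure from the default: Section 7.1 uses randomized subjects for disposition, and Section 13.2 limits the laboratory shift tables to subjects with both a baseline and a visit result.

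**The concern.** The default suits a measure taken in everyone. It does not suit one that part of the arm never receives by design. Under the Appendix 1 rule, a child of 8 is in the denominator of the C-SSRS and PHQ-8 percentages, and an adult is in the denominator of the CDI-2 percentages.

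These are not incidental tables. Protocol Section 2.3.2 reports more psychiatric adverse events with oral roflumilast than with placebo (5.9% versus 3.3%) and a small number of suicide-related cases. Protocol Sections 5.1.7 to 5.1.10 attach referral thresholds to the same instruments. A reader will take the printed percentage as the rate among those assessed, and it would be lower than that.

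**Working it through.** The SAP gives no computed figure on this point, so there is none to reproduce. The check is a denominator identity.

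**Formula.** Let *x* be the subjects meeting a criterion, *n* those assessed and *N* the Safety population in the arm.

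printed % = x / N = (x / n) × (n / N) = true rate × share assessed

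The relative understatement is therefore 1 − n/N.

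**PHQ-8, if tabulated separately from PHQ-A.** SAP Figure 1 caps adults: "Up to 50% of the subjects will be" 18 or older. So n/N is at most 0.50 for the trial as a whole.
- An assumed true rate of 4% prints as at most 4% × 0.50 = 2%.
- An assumed true rate of 10% prints as at most 10% × 0.50 = 5%.
- The supplied protocol (Section 4.2) has a cap of 25%, which would give 1% and 2.5%. The SAP states that it is based on Amendment 3, so its 50% is the figure to use.

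**Per-arm variation.** The cap is trial-wide, and randomization is stratified by vIGA-AD score and site, not by age. With 650 subjects split 2:1 (about 433 and 217) and exactly 325 adults, the hypergeometric 95% range for the adult share is 47-53% in the active arm and 45-55% in the vehicle arm. At the cap, one arm could sit slightly above one half.

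**C-SSRS, PHQ-A and CDI-2.** The documents do not give the 6-11 and 12-17 shares, so only an illustration is possible:

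| Assumed share assessed | Understatement (1 − share) | An assumed true 4% prints as |
|---|---|---|
| 80% | 20% | 3.2% |
| 50% | 50% | 2.0% |
| 30% | 70% | 1.2% |

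**Urinalysis.** Three limits apply. The shift tables already have their own restriction. Only the by-level percentages after Screening are exposed. Only under-12s who entered under Amendment 2 lack those samples, and their number is not given.

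**Between-arm comparison.** Take assumed true rates of 4% and 2% and a share of 0.50 in both arms. The printed rates are 2% and 1%. The difference falls from 2 points to 1 point, while the ratio stays at 2.

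**Visibility.** The PHQ and CDI-2 categories are exhaustive (they include the minimal and normal classes), so their counts add up to *n*, and x/n can be recovered from the same table. C-SSRS is tabulated as Yes responses only, so nothing in that table need reveal *n*.

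**The case against.** **The table shells may set the right denominator.** Section 5 says layouts are in a separate document, and the default yields where something else is specified. The shells were not available, so it cannot be said that the final tables will be wrong. But the SAP is the governing text, and it currently directs the whole-arm denominator. Unseen shells cannot be assumed to override it.

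**The age limits may count as specifying otherwise.** Sections 13.5 to 13.7 mention the ages for PHQ-A, CDI-2 and C-SSRS, and a programmer might take these as the table population. They say who completes each instrument, however, and do not set a denominator.

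**PHQ-8 and PHQ-A may share one table.** Section 13.5 treats them together, with one set of categories. If they are combined, the share assessed is that of all subjects aged 12 and over. A reader might infer that PHQ-8 rates are necessarily understated by at least half. The documents do not support that: it needs a separate table, and the 50% cap need not hold in each arm. This part of the objection stands.

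**Unassessed subjects are not scored as below the cut-off.** A reader might also infer that they are. For PHQ and CDI-2 they fall into no category, so the shortfall from 100% shows and can be corrected from the counts; Sections 13.6 and 5.6 also call for the number of subjects for CDI-2. This stands too, and it leaves C-SSRS as the place where the dilution could go unnoticed.

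**The consequence is limited.** Section 13 plans no formal safety inference, counts accompany most of the percentages, and between-arm ratios are roughly preserved. That is fair, and it bounds the importance of the point.

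**Conclusion.** The concern holds as a statement about the SAP text. The default puts never-assessed subjects in the denominator of the percentages in 13.5, 13.6, 13.7 and the by-level urinalysis table of 13.2, and nothing in those sections changes it. Printed percentages would equal the true rate times the share assessed.

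The one size that the documents support is for PHQ-8: about half the true rate or less overall, given a table separate from PHQ-A and the SAP's 50% adult cap, with slight variation by arm. The sizes for C-SSRS, PHQ-A, CDI-2 and urinalysis depend on age shares that the documents do not give. Absolute rates and absolute differences shrink, and ratios are roughly unchanged. A reader might go further and infer that a safety conclusion would change; nothing in the documents shows that. The point deserves correction chiefly because a diluted C-SSRS rate would look like an ordinary one.

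**What to change.** Add to SAP Sections 13.2 (by-level qualitative urinalysis), 13.5, 13.6 and 13.7:

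*Percentages are based on Safety population subjects with a non-missing result for that instrument or test at that visit (for shifts, at baseline and that visit).*

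Align the table shells with this. It is also worth stating whether PHQ-8 and PHQ-A are tabulated separately or together, and printing the number assessed beside the C-SSRS percentages.

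The cost is one sentence of SAP text per section and a programmed denominator. It needs no new data and leaves the efficacy analyses and the alpha allocation untouched.
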